10.6 Secondary Endpoint(s)

Linear mixed-effects models will be used to evaluate the following endpoints over time and determine the effect on PIVC indwell time for a given configuration (i.e., length/gauge):

- 1) cfHb concentration;
- 2) blood draw fill time;
- 3) blood flow velocities above or below the catheter
- 4) vessel dimensions; and
- 5) intravenous thrombus size.

Underlying normality assumptions will be verified and if not fulfilled non-parametric tests will be used. Multivariate analysis (to be defined in the SAP) will be employed to assess the effect of baseline characteristics on catheter indwell time and thus identify their power as predictive biomarkers using the following the independent variables including, but not limited to:

- 1) angle of insertion;
- 2) vessel dimension;
- 3) presence of side branches and/or intravenous valves;
- 4) age;
- 5) sex;
- 6) height;
- 7) weight;
- 8) BMI;
- 9) medical history questionnaire responses; and
- 10) exploratory endpoints.

A multiple-logistic regression analysis will be employed to assess the effect of baseline characteristics on catheter failure over a period of 72 hours and thus identify their power as predictive biomarkers using the independent variables including, but not limited to:

- 1) angle of insertion;
- 2) vessel dimension;
- 3) presence of side branches and/or intravenous valves;
- 4) age;
- 5) sex;
- 6) height;
- 7) weight;
- 8) BMI;
- 9) medical history questionnaire responses; and
- 10) exploratory endpoints.

A chi squared analysis will be employed to assess the proportion of individuals in each group (i.e., PIVC length and gauge) that have presence of the following at failure/end-of-protocol:

- 1) vein collapse;
- 2) intravenous thrombus; and

3) extravenuous thrombus.

All data will be evaluated using statistical modeling software (Prism, Release 8.3; GraphPad Software Inc., USA) or R (R 3.6.2 or higher). P-values ≤ 0.05 will be considered statistically significant.

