2.7 Study Procedure

The time-windows for collection of the primary, secondary and exploratory endpoints are detailed in Table 2.7.1.

The primary endpoint data (catheter dwell time) and exploratory endpoint data (PIVC complications) will be collected over 7 time-windows (see text highlighted in orange on Table 2.7.1). The secondary endpoint data (cfHb, blood draw time) will be collected over 8 discrete timepoints (including baseline, see text highlighted in red on Table 2.7.1).

All other secondary endpoint data (e.g., blood flow velocity, vessel diameter), except incidence of extravenous thrombus (assessed once the catheter is removed), will be collected over 15 timepoints (see text

highlighted in blue and grey on Table 2.7.1). Please note that the cells that indicate ‘Day’ in Table 1 are indicating the interventional visit days and are not inclusive of the screening visit or follow-up visit.

The flush pressure profile exploratory endpoint data will be collected over 7 timepoints (see text highlighted in blue on Table 2.7.1).

Table 2.7.1: List of sampling time points for primary, secondary, and exploratory endpoints. cfHb: cell-free hemoglobin; TIP: catheter tip position; BFV: blood flow velocity; C/V: catheter to vein ratio; PRES: in vivo pressure; PIVC: peripheral intravenous catheter; FILL: blood draw fill time. Time T+00:00 is the time of insertion

Day	Visit	Timepoint code	Approximate (hh:mm)	Time	Measurements taken
Day 1	Baseline	D1.1	T-00:60		TIP, BFV, C/V via ultrasound (no indwelling catheter)
		D1.2	T-00:40		cfHb via venipuncture
	Morning	D1.3	T+00:15		TIP, BFV, C/V via ultrasound, PRES via PIVC during flush
		D1.4	T+00:25		cfHb, FILL via PIVC
	Afternoon	D1.5	T+00:35		TIP, BFV, C/V via ultrasound
		D1.6	T+06:00		TIP, BFV, C/V via ultrasound, PRES via PIVC during flush
		D1.7	T+06:15		cfHb, FILL via PIVC
		D1.8	T+06:25		TIP, BFV, C/V via ultrasound
Day 2	Morning	D2.1	T+24:00		TIP, BFV, C/V via ultrasound, PRES via PIVC during flush
		D2.2	T+24:15		cfHb, FILL via PIVC
	Afternoon	D2.3	T+24:25		TIP, BFV, C/V via ultrasound
		D2.4	T+30:00		TIP, BFV, C/V via ultrasound, PRES via PIVC during flush
		D2.5	T+30:15		cfHb, FILL via PIVC
		D2.6	T+30:25		TIP, BFV, C/V via ultrasound
Day 3	Morning	D3.1	T+48:00		TIP, BFV, C/V via ultrasound, PRES via PIVC during flush
		D3.2	T+48:15		cfHb, FILL via PIVC
	Afternoon	D3.3	T+48:25		TIP, BFV, C/V via ultrasound
		D3.4	T+54:00		TIP, BFV, C/V via ultrasound, PRES via PIVC during flush

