2.8.3 Exploratory Endpoints

- Incidence of complications prompting device removal assessed by the frequency of occurrence of the following events:
 - Vein collapse
 - Phlebitis
 - Venous thrombosis
 - Dislodgement
 - Infiltration (called Extravasation in the protocol)
 - Accidental removal
- Manual flush variability will be evaluated using duration of flush and characteristics of Flush pressure profile (peak force) obtained on in-line pressure measurements

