6. Summary statistics and boxplot showing time between time of initial thrombus observation and device removal per device configuration

7. Importance of covariates will be computed with Boruta algorithm with a survival random forest model (an example output from the algorithm is provided in the Appendix by Figure B.7.1).
8. Test of predictive performance for the most important features (confirmed by the Boruta algorithm) using a leave-one-out strategy

In addition to the variables used in the primary endpoint survival model (device gauge and length), investigated baseline characteristics will be:

- Venous thrombosis
- Thrombus Length
- Thrombus Type
- Angles of insertion (Acute Inferior and Superior)
- Catheter to vein (C/V) ratio
- Catheter length in vessel
- Presence of side branches and/or intravenous valves
- Age
- Gender
- Height
- Weight
- BMI
- Dominant arm
- Medical history questionnaire responses
- Exploratory endpoints:
 - Vein collapse
 - Phlebitis
 - Dislodgement
 - Extravasation
- item Screening Blood Testing (as provided by Blood Testing CRF)
 - Coagulation Panel: PT & aPTT
 - Platelet Aggregometry: ADP, TRAP & Collagen Induced Maximal Amplitude
 - Blood Screening: Blood Glucose & Triglycerides
 - Liver Panel: ALT Average Measurement & AST Average Measurement

The Boruta algorithm does not require specific formatting and generally works well with continuous and categorical variables. In some cases, it might be interesting to move from continuous format to a categorical one (e.g. age) depending on the final analysis. Categorization rules will be detailed whenever performed.

5.2.2.4 Evaluation of changes in vessel dimensions, PIVC position (insertion angle and *in situ* tip position), and haemodynamics from baseline throughout indwell time

These will be evaluated using:

- C/V ratio
- Catheter Length in Vessel (mm)
- Catheter Insertion Angle - acute inferior border angle (deg)
- Catheter Insertion Angle - acute superior border angle (deg)
- Blood Draw Time (sec)
- Blood Flow Velocity (cm/sec)
- *In situ* tip position (Mid-Stream & Wall Contact)

For each of these characteristics, summary statistics by indwell time considered as a discrete variable (0, 6, 24, 30, 48, 54, 72 hours) and line and bar plots will be generated on average for continuous and by proportion for categorical responses, respectively.

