6.3 Demographics and Baseline Variables

Demographic variables will include all medical history questionnaire responses, and each of the following variables at time of intervention:

- Age
- Height
- Weight
- Resting blood pressure
- Gender
- BMI
- Menstrual cycle phase (women only)

Table A.1.1 provides an example of demographic variables summary table, per study group and overall.

Baseline variables will include all sonographic data prior to PIVC insertion and cfHb collected via

venipuncture. Tables A.3.1 and A.3.2 provide examples of baseline variables summary table, per study group and overall, including blood analysis.

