Min, Max	18, 27	19, 27	18, 27
Total Count	20	20	40

A.2 Family Medical History

Table A.2.1: Numerical Summary of Family Medical History, per Group (i.e. Gauge) and Overall

Characteristic	20G	22G	Overall
Blood Disorder or Bleeding or Clotting Problem			
No	20 (100.0%)	18 (90.0%)	38 (95.0%)
Yes	0 (0.0%)	2 (10.0%)	2 (5.0%)
Total	20	20	40

Table A.2.1: Numerical Summary of Family Medical History, per Group (i.e. Gauge) and Overall continued

Characteristic	20G	22G	Overall
Cancer			
No	19 (95.0%)	19 (95.0%)	38 (95.0%)
Yes	1 (5.0%)	1 (5.0%)	2 (5.0%)
Total	20	20	40
Heart Disease			
No	20 (100.0%)	20 (100.0%)	40 (100.0%)
Yes	0 (0.0%)	0 (0.0%)	0 (0.0%)
Total	20	20	40
High Blood Pressure (Hypertension)			
No	13 (65.0%)	19 (95.0%)	32 (80.0%)
Yes	7 (35.0%)	1 (5.0%)	8 (20.0%)
Total	20	20	40
Diabetes Type 2			
No	19 (95.0%)	14 (70.0%)	33 (82.5%)
Yes	1 (5.0%)	6 (30.0%)	7 (17.5%)
Total	20	20	40

A.3 Baseline Characteristics

Table A.3.1: Numerical Summary of Baseline PIVC Characteristics, per Group (i.e. Gauge) and Overall

Characteristic	20G	22G	Overall
Tip Position Mid-Stream			
Yes	16 (80.0%)	15 (75.0%)	31 (77.5%)
No	4 (20.0%)	5 (25.0%)	9 (22.5%)
Total	20	20	40
Tip Position Well Contact			
No	16 (80.0%)	17 (85.0%)	33 (82.5%)
Yes	4 (20.0%)	3 (15.0%)	7 (17.5%)
Total	20	20	40
Blood Flow Velocity (cm/sec)			
Mean	161.94	161.86	161.90
95% Mean CI	159.06, 164.96	159.05, 164.73	159.86, 163.97
Median	160.97	162.27	161.69
SD	6.90	6.61	6.67
Min, Max	150.46, 173.71	150.97, 173.28	150.46, 173.71
Total Count	20	20	40
Catheter-to-Vein ratio			
Mean	38.70	35.92	37.31
95% Mean CI	36.95, 40.42	34.27, 37.56	36.02, 38.61
Median	38.88	35.06	36.93
SD	4.13	3.91	4.21
Min, Max	32.11, 44.91	30.23, 42.67	30.23, 44.91
Total Count	20	20	40

Table A.3.2: Numerical Summary of Baseline Venipuncture Blood Analysis, per Group (i.e. Gauge) and Overall

Tube Volume	Characteristic	20G	22G	Overall
2mL	cfHb (mg/dL)			
	Mean	199.31	200.93	200.12
	95% Mean CI	175.48, 222.22	174.31, 228.18	182.19, 218.30
	Median	201.03	199.82	199.82
	SD	53.78	64.40	58.57
	Min, Max	56.99, 324.24	111.27, 317.8	56.99, 324.24
	Total Count	20	20	40

Table A.3.2: Numerical Summary of Baseline Venipuncture Blood Analysis, per Group (i.e. Gauge) and Overall continued

Tube Volume	Characteristic	20G	22G	Overall
	Haemolysis - AU480 (Yes/No)			
	No	10 (50.0%)	10 (50.0%)	20 (50.0%)
	Yes	10 (50.0%)	10 (50.0%)	20 (50.0%)
	Total	20	20	40
	Haemolysis - Visual (Yes/No)			
	Yes	14 (70.0%)	12 (60.0%)	26 (65.0%)

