	No	6 (30.0%)	8 (40.0%)	14 (35.0%)
	Total	20	20	40
	Blood Draw Fill Time (sec)			
	Mean	39.48	39.15	39.31
95% Mean CI	37.86, 41.08	37.41, 40.86	38.10, 40.51	
Median	39.40	39.92	39.74	
SD	3.83	4.06	3.90	
Min, Max	32.77, 46.32	32.06, 46.4	32.06, 46.4	
Total Count	20	20	40	
6mL	cfHb (mg/dL)			
	Mean	194.94	200.96	197.95
	95% Mean CI	174.19, 215.28	178.16, 223.07	182.86, 213.25
	Median	212.88	193.48	207.24
	SD	47.91	52.64	49.77
	Min, Max	86.01, 275.98	103.33, 311.35	86.01, 311.35
	Total Count	20	20	40
	Haemolysis - AU480 (Yes/No)			
	Yes	12 (60.0%)	9 (45.0%)	21 (52.5%)
	No	8 (40.0%)	11 (55.0%)	19 (47.5%)
Total	20	20	40	
Haemolysis - Visual (Yes/No)				
Yes	13 (65.0%)	13 (65.0%)	26 (65.0%)	
No	7 (35.0%)	7 (35.0%)	14 (35.0%)	
Total	20	20	40	
Blood Draw Fill Time (sec)				
Mean	99.94	101.73	100.83	
95% Mean CI	97.33, 102.41	98.61, 105.01	98.85, 102.95	
Median	101.04	100.15	100.15	
SD	5.98	7.49	6.75	
Min, Max	86.61, 108.96	91.1, 116.4	86.61, 116.4	
Total Count	20	20	40	

A.4 Indwell Time

Table A.4.1: Numerical Summary of Subjects Indwell Time in hours, per Device Configuration (Gauge and Length) and Overall

Characteristic	BD Nexiva (22G x 1 inch)	BD Nexiva (22G x 1.75 inch)	BD Nexiva (20G x 1 inch)	BD Nexiva (20G x 1.75 inch)	Overall
Indwell Time (Hours)					
Mean	44.76	55.84	59.72	69.82	57.54
95% Mean CI	36.08, 53.42	45.68, 64.78	52.74, 65.55	68.08, 71.24	53.19, 61.60
Median	42.84	66.22	64.09	72.00	66.97
SD	20.38	22.59	14.76	3.83	18.97
Min, Max	9.4, 72	0.07, 72	15.76, 72	58.6, 72	0.07, 72
Total Count	20	20	20	20	80

Table A.4.2: Proportional Hazard Ratios computed from Cox Proportional Hazards model for Indwell time

	HR(95%CI)	P(Wald's test)	P(LR-test)
device: ref.=BD Nexiva (22G x 1 inch)			0.002
BD Nexiva (22G x 1.75 inch)	0.6 (0.28,1.26)	0.175	
BD Nexiva (20G x 1 inch)	0.57 (0.27,1.2)	0.141	
BD Nexiva (20G x 1.75 inch)	0.2 (0.08,0.49)	< 0.001	

A.5 Indwell Failure Mode

Table A.5.1: Failure Modes Count Overall

Failure Mode	Flush	Draw (2mL)	Draw (6mL)
Unsecure Luer Connection	2	0	1
Locked Clamps	2	0	0
Catheter Dislodgement	5	0	0
Catheter Kinking	2	2	0
Vasospasm	0	0	0
Thrombus	24	10	7
Infiltration	2	0	0
Other	9	0	1

A list of the failure modes available in the free form text field describing the “Other” category will be provided.

Table A.5.2: Failure Modes Count Per Device Configuration

Device	Failure Mode	Flush	Draw (2mL)	Draw (6mL)
BD Nexiva (22G x 1 inch)	Luer Connection	0	0	0
	Clamp	1	0	0
	Tube Kinking	0	0	0
	Dislodgement	0	0	0
	Catheter Kinking	1	0	0

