	BD Nexiva (22G x 1 inch) - BD Nexiva (20G x 1.75 inch)	4.98	-0.79	10.75	0.118	NS
	BD Nexiva (22G x 1.75 inch) - BD Nexiva (20G x 1 inch)	3.04	-2.32	8.41	0.462	NS
	BD Nexiva (22G x 1.75 inch) - BD Nexiva (20G x 1.75 inch)	5.23	-0.07	10.54	0.054	NS
	BD Nexiva (20G x 1 inch) - BD Nexiva (20G x 1.75 inch)	2.19	-2.86	7.24	0.679	NS
48	BD Nexiva (22G x 1 inch) - BD Nexiva (22G x 1.75 inch)	-2.76	-9.66	4.13	0.73	NS
	BD Nexiva (22G x 1 inch) - BD Nexiva (20G x 1 inch)	-0.63	-7.46	6.20	0.995	NS
	BD Nexiva (22G x 1 inch) - BD Nexiva (20G x 1.75 inch)	-1.11	-7.71	5.50	0.973	NS
	BD Nexiva (22G x 1.75 inch) - BD Nexiva (20G x 1 inch)	2.13	-3.54	7.81	0.766	NS
	BD Nexiva (22G x 1.75 inch) - BD Nexiva (20G x 1.75 inch)	1.66	-3.73	7.05	0.857	NS
	BD Nexiva (20G x 1 inch) - BD Nexiva (20G x 1.75 inch)	-0.48	-5.76	4.80	0.996	NS
54	BD Nexiva (22G x 1 inch) - BD Nexiva (22G x 1.75 inch)	-0.78	-8.55	6.98	0.994	NS
	BD Nexiva (22G x 1 inch) - BD Nexiva (20G x 1 inch)	2.87	-5.01	10.75	0.784	NS
	BD Nexiva (22G x 1 inch) - BD Nexiva (20G x 1.75 inch)	3.35	-4.08	10.78	0.651	NS
	BD Nexiva (22G x 1.75 inch) - BD Nexiva (20G x 1 inch)	3.65	-2.66	9.96	0.443	NS
	BD Nexiva (22G x 1.75 inch) - BD Nexiva (20G x 1.75 inch)	4.13	-1.60	9.87	0.248	NS
	BD Nexiva (20G x 1 inch) - BD Nexiva (20G x 1.75 inch)	0.48	-5.38	6.35	0.997	NS
72	BD Nexiva (22G x 1 inch) - BD Nexiva (22G x 1.75 inch)	-6.57	-15.81	2.67	0.258	NS
	BD Nexiva (22G x 1 inch) - BD Nexiva (20G x 1 inch)	-2.76	-11.75	6.24	0.859	NS
	BD Nexiva (22G x 1 inch) - BD Nexiva (20G x 1.75 inch)	-1.09	-9.40	7.22	0.987	NS
	BD Nexiva (22G x 1.75 inch) - BD Nexiva (20G x 1 inch)	3.82	-4.35	11.99	0.624	NS
	BD Nexiva (22G x 1.75 inch) - BD Nexiva (20G x 1.75 inch)	5.48	-1.92	12.88	0.225	NS
	BD Nexiva (20G x 1 inch) - BD Nexiva (20G x 1.75 inch)	1.67	-5.42	8.75	0.93	NS

A.10 Thrombus Occurrence

Table A.10.1: Numerical Summary of Thrombus Occurrence, per Device Configuration (Gauge and Length) and Overall

Characteristic	BD Nexiva (22G x 1 inch)	BD Nexiva (22G x 1.75 inch)	BD Nexiva (20G x 1 inch)	BD Nexiva (20G x 1.75 inch)	Overall
Thrombus (Yes/No)					
Yes	62 (63.3%)	72 (62.1%)	99 (79.8%)	68 (49.3%)	301 (63.2%)
No	36 (36.7%)	44 (37.9%)	25 (20.2%)	70 (50.7%)	175 (36.8%)
Total	98	116	124	138	476

Table A.10.2: Numerical Summary of Thrombus Analysis, for each time point, per Device Configuration (Gauge and Length) and Overall

[figure not shown]

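### SAP 5.2.2.3 lists events that arise during dwell as baseline predictors of indwell time, with no measurement time, and two of them partly restate the outcome

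*SAP*

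**What the plan says.** Item 7 of SAP 5.2.2.3 ranks covariates for indwell time with the Boruta algorithm around a survival random forest. The covariate list opens with "In addition to the variables used in the primary endpoint survival model (device gauge and length), investigated baseline characteristics will be". Alongside true pre-insertion items (age, BMI, screening blood tests) it contains venous thrombosis, thrombus length and type, vein collapse, phlebitis, dislodgement and extravasation. No visit, landmark or coding rule is attached to any of them.

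Other sections treat these items as events during dwell. SAP 2.7 says "exploratory endpoint data (PIVC complications) will be collected over 7 time-windows", the same windows as for dwell time. SAP 2.8.3 counts them as complications that lead to removal. Items 2 and 6 of 5.2.2.3 measure the time from first sighting of a thrombus to removal.

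The word baseline does not settle the matter. SAP 6.3 says "Baseline variables will include all sonographic data prior to PIVC insertion", but Table A.3.1, "Numerical Summary of Baseline PIVC Characteristics, per Group (i.e. Gauge) and Overall", includes tip position, which exists only once the catheter is in place.

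On overlap with the outcome, SAP 5.2.1.1 defines the event by failed flush or failed blood draw. The table that counts the modes of those failures ("Table A.5.1: Failure Modes Count Overall") has rows for catheter dislodgement and infiltration. SAP 2.8.3 equates infiltration with extravasation: "Infiltration (called Extravasation in the protocol").

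Three nearby provisions bear on timing. Protocol 10.7 admits exploratory endpoints only as collected at baseline, but for the regression in Protocol 10.6. The chi-squared analysis in Protocol 10.6 compares the proportions of individuals "that have presence of the following at failure/end-of-protocol", including intravenous thrombus. SAP 5.2.3.1 uses the same kinds of event as predictors in a further survival forest and adds a Boruta run at each time point.

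**The concern.** There are two separate faults.

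The first is circular meaning. A catheter recorded as dislodged or infiltrated when a flush fails has, by that record, failed. Using the flag to predict failure time says little about cause. Read literally at baseline, both flags would be nearly constant just after a successful insertion, so they make sense on the list mainly as during-dwell status.

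The second is timing. If a thrombus is coded as ever seen during dwell, a catheter that lasts 72 h has up to seven pre-flush assessments at which it can turn positive, and one that fails early has few. The predictor then carries information about the outcome even if thrombus has no effect.

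Item 7 is the factor ranking for a secondary objective. SAP 2.6 names it twice in the preliminary analysis that precedes database lock, and the final analysis has the same gap.

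**Working it through.** **1. Design figure.** Inputs from SAP 2.4: medians 1 and 3 days, 3 days of follow-up, 19 and 20 catheters, two-sided alpha 0.05. With exponential survival, failure by 72 h is 1 − 2^(−3) = 0.875 and 1 − 2^(−1) = 0.50. Expected events are 19 × 0.875 + 20 × 0.50 = 26.6. The Lakatos log-rank calculation gives power 0.8056 against the stated 0.8054, so the failure model below matches the SAP's.

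**2. Mechanism.** Assume thrombus onset is exponential with median 48 h and unrelated to failure. The chance of onset by time t is 1 − 2^(−t/48): 0.29 at 24 h and 0.65 at 72 h. Long-lasting catheters are therefore more often thrombus-positive with no effect at all.

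**3. No true effect, ever/never coding, Cox model.** Common inputs: 80 catheters, medians 24 and 72 h, administrative end at 72 h, the seven visits of SAP Table 2.7.1. Thrombus frequency is assumed because the documents give only dummy data. Set A adjusts for length and gauge; Set B uses thrombus alone. Each has 1000 trials per scenario.

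| Set | Ever seen | Median or apparent HR | Significant at 0.05 |
|---|---|---|---|
| A | 60 / 40 / 20% | 0.38 / 0.48 / 0.56 | 91 / 70 / 31% |
| A | 10 / 5% | 0.57 / 0.61 | 8 / 2% |
| B | 67 / 45 / 27% | 0.37 / 0.47 / 0.54 | 96 / 80 / 45% |
| B | 12% | 0.57 | 14% |

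In Set A with equal 72 h medians, the rates at 60/40/20% become 79/51/17%. If half the catheters already have thrombus at insertion, the rate is 18%.

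**4. True harm, ever/never coding.** Set A, true HR 2, frequency 20/40/60%: the median HR appears as 0.86/0.75/0.60 and is never significantly harmful. Time-updated coding from the same-visit scan finds the harm in 37/51/52% of trials.

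**5. Properly timed coding, no true effect.** At 20-60% frequency in Set A, the 24 h landmark is significant in 4.3-6.3% of trials and same-visit time-updated coding in 4.3-5.1%. With participant-clustered standard errors these become 4.8-9.2% and 5.4-8.2%.

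**6. Forest.** Boruta was approximated twice with different settings, since the SAP gives none.

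- Set A, no effect: confirmed in 73/80 trials at 62% frequency, 58/80 at 40%, 16/80 at 20%, 1/40 at 10%.
- Set B, no effect (40 runs each): 65% at 67% frequency, 27.5% at 45%, 12.5% at 27%, 2.5% at 12%.
- Set B, no effect, thrombus fixed at insertion with 45% prevalence: 0%.
- True HR 3, ever/never: 1/40 in Set A (40% frequency) and 5% in Set B (45%). An insertion-time thrombus with HR 3 and 45% prevalence was confirmed in 37.5% of Set B runs.

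Monte Carlo error for 40 runs is at most √(0.25/40), about 8 points.

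**7. Overlap.** Table A.5.1 (dummy data) sums to 67 failure records. Dislodgement has 5 (7.5%) and infiltration 2 (3.0%), together 7/67 = 10.4%. With dislodgement causing 8% of failures, Set A confirmed the flag in 16/280 trials. Set B, at 7.5% and 3%, confirmed neither flag in any run. Set A reached 23/80 and 50/80 only when dislodgement caused 20% and 30% of failures.

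**The case against.** The list is headed baseline, Protocol 10.6 uses the same label, and Protocol 10.7 restricts exploratory endpoints to baseline collection. On that reading thrombus is taken at a post-insertion scan, for which Table A.10.2 ("Numerical Summary of Thrombus Analysis, for each time point, per Device Configuration (Gauge and Length) and Overall") has a time 0 row, and the timing bias disappears. SAP 5.2.3.1 also plans Boruta at each time point. The study is a feasibility study with no acceptance criteria (SAP 2.9), pre-lock results are provisional, and items 2-4 and 6 display thrombus against time.

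Part of this stands. Protocol 10.7 shows intent, but it governs the protocol's regression and the SAP does not carry it into item 7. The per-time-point Boruta limits the response to failures up to that time; it does not limit predictors to earlier values, and it does not govern item 7. The baseline reading also leaves dislodgement and extravasation without a useful role. The feasibility setting limits the consequence.

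Three stronger readings are tempting and not supported:

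- **That the SAP will code thrombus over the whole dwell.** It does not say so. The failure/end-of-protocol status in Protocol 10.6 belongs to a different analysis.
- **That the same data would give opposite rankings under different codings.** The forest results compare different true effects under ever/never coding, or thrombi arising at different times. No single data set was ranked under two codings.
- **That dislodgement will dominate the ranking.** Near the only frequencies in the documents, themselves dummy values, it was confirmed rarely or never.

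**Conclusion.** The point holds and should be corrected before the analysis. The list mislabels during-dwell events as baseline, item 7 gives no measurement time, and two predictors partly restate the outcome. For those two the fault is one of meaning, with little numerical effect at dummy-table frequencies.

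For thrombus the size is conditional. Under whole-dwell coding, 20-60% frequency and the SAP's medians, a null factor looks protective and real harm is hidden or reversed in Cox models. The approximate forests agree in direction, with false confirmation of roughly 13-91% at 20-67% frequency. That width reflects Boruta settings the SAP does not give, so only the direction is firm. At about 5-12% frequency the forest effect is small. Onset times, frequencies and effects are all assumptions.

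The harm is to the factor ranking. It does not extend to the primary comparison or to the thrombus displays over time.

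**What to change.** 1. In item 7, state that every predictor is fixed before insertion or at the D1.3 scan, in line with Protocol 10.7. That scan precedes the first monitored flush and first draw but follows the post-cannulation flush (Protocol 7.2).
2. Analyse thrombus presence, length and type, vein collapse and phlebitis by landmark (for example 6 and 24 h) or as time-updated covariates in a participant-clustered Cox model, using the latest assessment before that visit's flush and draw. Protocol 7.4 and 7.10.1 already place scans before flushing and collection, and site checks before each draw.
3. Remove dislodgement and extravasation from the item 7 predictors and report them descriptively as failure modes. Record this as a departure from Protocol 10.6, which names exploratory endpoints among its independent variables. In SAP 5.2.3.1, state that the removal reasons Flush Failure and Blood Draw Failure are not forest predictors.

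**Cost.** SAP wording and modest programming, with no new data. Thrombus during dwell leaves the joint ranking. Power is limited (37-52% for HR 2 with same-visit coding), and clustered standard errors with 40 participants are slightly liberal. Late landmarks leave few events. With 40 catheters per length, the number at risk at time t (in hours) is 40 × 2^(−t/24) + 40 × 2^(−t/72), and expected survivors at 72 h are 5 + 20 = 25. Events remaining are about 71 − 25 = 46 after 6 h, 52 − 25 = 27 after 24 h and 35 − 25 = 10 after 48 h.

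Two separate minor clarifications belong in the same edit. Item 8 should say whether Boruta is rerun in each fold and whether a catheter or a participant is left out. Tip location and vein depth appear in the section title but not in the list.
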